#### **3.2 Secondary Objectives**

The secondary objective is to compare the acute effects of a single administration oxytocin vs. placebo, to the clinical and behavioral effects of chronic OT treatment vs. placebo in schizophrenia participants. The study will assess the effects of exogenous oxytocin on laboratory-based social interactions, Theory of Mind (ToM), and negative symptoms in participants with schizophrenia.

### **4 STUDY DESIGN**

#### **4.1 Study Overview**

100 subjects are planned. During the fMRI phase, intranasal oxytocin and placebo will be administered to each subject in a randomized, double-blind, counterbalanced order with a cross-over design, at least one week apart. Testing will commence 45 minutes after drug administration and continue for no longer than 3 hours.

During the longitudinal phase, participants will then be randomized to receive approximately three weeks (18-24 day range) of twice daily administration of either OT or placebo. Testing will commence on baseline and after three weeks (18 to 24 days) of drug administration.

Screening data will be reviewed to determine subject eligibility. Subjects who meet all inclusion criteria and none of the exclusion criteria will be entered into the study.

The following treatment regimens will be used:

- Experimental treatment: Intranasal oxytocin
- Placebo: Saline solution

Total duration of subject participation will be 15 hours over 2 months.

---

## 5 CRITERIA FOR EVALUATION

### 5.1 Primary Efficacy Endpoint

The primary efficacy endpoint will be social functioning measured by the Social Functioning Scale (SFS). SFS is one of the most commonly used social functioning measures in schizophrenia research, yields good information about abilities and activities, and is reliable, valid, and sensible and responsive to change. The endpoint will be assessed from baseline to end of the task. We will also assess activation of the rTPJ during social cognitive tasks measured with fMRI.

### 5.2 Secondary Efficacy Endpoints

- Social skills will be assessed during the chronic period over the phone or video chat. Participants will answer questions about their social interactions and experiences.
- Theory of Mind (ToM) will be assessed using The Hinting Task a well validated audiovisual tool that incorporates social inferences. The endpoint will be assessed from baseline to end of the task.
- Negative symptoms will be assessed with Clinical Assessment Interview for Negative Symptoms (CAINS), comprising two subscales reflecting the negative symptom factors. - The endpoint will be assessed from baseline to end of the task.

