#### **10.4 Visit 4 (Week 3)**

1. Urine Pregnancy Test
2. Record changes to concomitant medications.
3. Record participant weight
4. ToM, negative and positive symptoms, and social ability assessments
5. Oxytocin/placebo administration
6. Oxytocin self-administration training.

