### **12.4 Analysis of Secondary Endpoints**

Similar analyses as stated in 15.3 will be conducted for the secondary clinical outcomes including social ability, negative symptoms (CAINS), and ToM(Hinting Task).

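### The social secondary outcome is named and timed inconsistently, so it is unclear whether the endpoint is the remote questions or the in-person Visit 4 to Visit 5 measure

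*Combined protocol and SAP*

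**What the plan says.** **Objective.** Section 3.2 sets out to assess the "effects of exogenous oxytocin on laboratory-based social interactions, Theory of Mind (ToM), and negative symptoms".

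**Declared endpoint.** The synopsis lists social skills, negative symptoms and theory of mind as the secondary endpoints. Section 5.2 describes the first of these: "Social skills will be assessed during the chronic period over the phone or video chat". It adds: "Participants will answer questions about their social interactions and experiences". The Hinting Task and CAINS bullets beside it each carry the sentence "The endpoint will be assessed from baseline to end of the task". The social skills bullet does not.

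**Analysis.** Section 12.4 applies analyses similar to the primary one to "secondary clinical outcomes including social ability, negative symptoms (CAINS), and ToM(Hinting Task"). The synopsis statistics row also says social ability. The primary analysis in 12.3 is a linear regression of SFS change on a drug-versus-placebo indicator, and no covariate is named. Section 12.4 cites a section 15.3, which does not exist.

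**Schedule.** Section 10.4 (Visit 4) lists "ToM, negative and positive symptoms, and social ability assessments" ahead of that visit's dosing, and 10.6 (Visit 5) lists the same assessments. Section 9.1.6 puts social ability among the measures completed in the laboratory. In the chronic period, 10.5 lists a social functioning assessment, not social skills. Appendix 1 marks social functioning tests at Visits 1, 4 and 5.

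**The concern.** The declared endpoint and the analysed outcome differ in mode and timing as well as in name. One is collected by phone or video while participants are on study drug. The other is collected in person before and after the chronic course. Neither is described as a laboratory interaction, which is what 3.2 says will be studied.

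Two analysts following the plan could therefore produce different social secondary results. One would analyse the remote answers because 5.2 declares them. The other would analyse the Visit 4 to Visit 5 change because 12.4 names that outcome. Each could claim compliance, and the two need not agree in size or direction. Section 12 defers detail to an SAP written before the final analysis, but 12.5 has interim analyses starting once 60 participants have completed. The outcome is better fixed before such data have been seen.

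**Working it through.** The plan gives no effect size, standard deviation or power for the social secondary outcome, so there is no figure to reproduce. The main check sets the sections side by side.

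| Place | Label | Mode | Timing | Baseline stated |
|---|---|---|---|---|
| 3.2 | laboratory-based social interactions | laboratory | not given | no |
| 5.2; synopsis objectives and endpoints rows | social skills | phone or video | chronic period | no |
| 9.1.6 | social ability | laboratory | not given | no |
| 10.4, 10.6 | social ability | in-person visits | Visits 4 and 5 | yes, by schedule |
| 10.5 | social functioning | remote | chronic period | no |
| 12.4; synopsis statistics row | social ability | not given | not given | implied by a change-type analysis |
| Appendix 1 | social functioning tests | not given | Visits 1, 4 and 5 | yes, by schedule |

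Three things follow.

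1. No section describes an interaction task, so nothing listed directly measures the construct in 3.2.
2. The outcome in 12.4 has a Visit 4 value, listed before dosing, and a Visit 5 value. The visit plan therefore supports a change analysis of social ability.
3. The endpoint in 5.2 has no stated baseline, instrument, score or fixed time point.

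A second check shows what a baseline is worth. **Assumptions:** the outcome has the same variance σ² at baseline and follow-up, in both arms, with correlation ρ between the two. The documents give no ρ, so 0.5, 0.7 and 0.8 are illustrative. The variance of the treatment comparison is proportional to:

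- follow-up value only: σ²
- unadjusted change score (the 12.3 template): 2σ²(1 − ρ)
- baseline-adjusted analysis: σ²(1 − ρ²)

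The participants needed for equal precision scale with these variances.

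| ρ | Change, 2(1 − ρ) | Adjusted, 1 − ρ² | Follow-up only ÷ change | Change ÷ adjusted |
|---|---|---|---|---|
| 0.5 | 1.00 | 0.75 | 1/1.00 = 1.0 | 1.00/0.75 = 1.33 |
| 0.7 | 0.60 | 0.51 | 1/0.60 = 1.67 | 0.60/0.51 = 1.18 |
| 0.8 | 0.40 | 0.36 | 1/0.40 = 2.5 | 0.40/0.36 = 1.11 |

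These ratios compare analyses of a single measure. They do not compare the remote measure with the in-person one, whose variances and sensitivity to treatment are unknown.

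**The case against.** The strongest reply is that this is loose naming of one outcome. The synopsis lists three secondary endpoints (social skills, negative symptoms, theory of mind) and 12.4 lists three (social ability, CAINS, Hinting Task), which pair off one to one. Section 4.1 also says of the longitudinal phase: "Testing will commence on baseline and after three weeks (18 to 24 days) of drug administration". That reading is plausible, but it does not settle the point. If the two are one outcome, 5.2 contradicts 10.4 and 10.6 on how and when it is collected, and the plan never says which governs.

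Several stronger readings are tempting but unsupported:

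- **That the social endpoint has no baseline and cannot be analysed.** The outcome 12.4 names has a Visit 4 value. Sections 4.1, 10.1 (social functioning assessments at Visit 1) and 10.5, with Appendix 1, leave open an earlier counterpart to the remote questions. Even with no baseline, a randomized comparison of on-treatment values would be valid.
- **That the remote questions are self-report and cannot reflect skill.** Section 5.2 says participants answer questions. It does not say whether they rate themselves or an interviewer scores the answers.
- **That the sponsor means to choose the favourable result.** The wording leaves the choice open, but nothing in the documents shows intent.
- **That a missing baseline is necessarily costly.** Against the change score in 12.3, it costs nothing at ρ = 0.5.

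The planned SAP could resolve the ambiguity, but it would not by itself correct the protocol's endpoint list.

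**Conclusion.** The point holds as an inconsistency in definition. The objective, the declared endpoint and the analysed outcome do not match, no instrument or score is named for social skills or social ability, and the plan does not say whether the remote measure or the Visit 4 to Visit 5 measure is the secondary endpoint. It affects one of three secondary endpoints and should be corrected; the primary endpoint is unaffected.

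This conclusion rests on the text alone. The precision figures are illustrative and depend on the assumed correlations and equal variances. Under those assumptions, follow-up values alone need 1.0 to 2.5 times the participants of the unadjusted change score, and that change score needs 1.33 to 1.11 times those of a baseline-adjusted analysis, as ρ goes from 0.5 to 0.8.

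**What to change.** 1. In 5.2 and the synopsis, declare the in-person social ability assessment as the social secondary endpoint. The sponsor must supply the instrument and score, since the documents give neither.
2. In 12.4, define the analysis as change from the pre-dose Visit 4 value to Visit 5, with the Visit 4 value as covariate. The covariate goes beyond the 12.3 template, but it uses a value already scheduled and improves precision at each correlation examined.
3. Give the phone or video questions a separate, supportive role with stated content, scoring and timing. If no baseline for them is already taken, ask them once at Visit 4 before the first chronic dose.
4. Reword 3.2 to name the construct these instruments measure. Align 10.5 and Appendix 1 with the chosen labels, and correct the reference to section 15.3.

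The cost is a wording amendment and, at most, a few extra minutes at an existing visit. No additional participants or visits are needed.

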### 5.3 Safety Evaluations

- No serious adverse effects have been demonstrated in studies examining intranasal administration of OT in numerous patient and healthy populations. Therefore, we don't predict any serious adverse events to occur during this study. Documented side effects include runny, stuffy, or irritated nose, and more rarely, nausea and vomiting. Participants may experience distress due to the nature of personal questions about mental health, substance use, and life experiences. They may also experience anxiety and/or fatigue due to the length of the study days.

### 5.4 Other Evaluations (include only if applicable)

- Positive symptoms will be assessed with the 34-item, interview-based, Scale for the Assessment of Positive Symptoms, which focuses on hallucinations, delusions, disorganized behavior and thought disorder
- Quality of life will be assessed with the Quality of Life Scale (QLS), a 7-item assessment that measures domains such as interpersonal relations, occupation role functioning and intrapsychic foundations

- The Experience in Close Relationships (ECR) questionnaire is a 9-item questionnaire that will be used to assess attachment style in respect to a variety of close relationships.

## 6 SUBJECT SELECTION

### 6.1 Study Population

Subjects with a diagnosis of schizophrenia, schizoaffective, schizophreniform disorder, or brief psychotic disorder, who meet the inclusion and exclusion criteria will be eligible for participation in this study.

### 6.2 Inclusion Criteria

1. Veteran
2. Male or female  $18 \geq 70$  years of age at Visit 1.
3. Must comprehend English
4. Meet DSM-V criteria for schizophrenia, schizophreniform, schizoaffective disorder, or brief psychotic disorder.
5. Clinically stable, no medication changes or psychiatric hospitalizations in past month
6. Social Functioning Scale raw score  $\leq 75$
7. Written informed consent obtained from subject or subject's legal representative and ability for subject to comply with the requirements of the study.

### 6.3 Exclusion Criteria

1. Active substance use disorder in the past month – except Mild to Moderate Cannabis use disorder.
2. Significant neurological/medical disorder
3. Pacemaker, extensive dental work, or any metal implants
4. Claustrophobia, deafness, or inability to read
5. Current participation in a psychosocial intervention
6. Taking high dose of testosterone, estrogen/progesterone

7. Pregnant, breastfeeding, or unwilling to practice birth control during participation in the study.
8. Presence of a condition or abnormality that in the opinion of the Investigator would compromise the safety of the participant or the quality of the data.
9. Congestion or sinus problems that could interfere with the study as per the opinion of the investigator

## 7 CONCURRENT MEDICATIONS

All subjects should be maintained on the same medications throughout the entire study period, as medically feasible, with no introduction of new chronic therapies.

### 7.1 Allowed Medications and Treatments

Standard therapy for schizophrenia is allowed except for treatments noted in the exclusion criteria described above and as noted in the prohibited medications section below.

### 7.2 Prohibited Medications and Treatments

The following medications are prohibited during the study and administration will be considered a protocol violation.

- High dose testosterone or estrogen/progesterone

## 8 STUDY TREATMENTS

### 8.1 Method of Assigning Subjects to Treatment Groups

Randomization sequences will be generated using a response adaptive randomization study design. Enrollment would end when at least 55 participants have been assigned to the drug treatment arm and 40 participants have been assigned to the placebo arm.

## 8.2 Blinding

Due to the objectives of the study, the identity of test and control treatments will not be known to investigators, research staff, or participants. The following study procedures will be in place to ensure double-blind administration of study treatments.

- Access to the randomization code will be strictly controlled.
- Packaging and labeling of test and control treatments will be identical to maintain the blind. The oxytocin or placebo will be repackaged into smaller bottles containing 1 mL of either the oxytocin or placebo. Designated study staff, who will not be present during the study sessions and will not be involved with running any of the study sessions, will be responsible for repackaging the drugs and keeping track of each bottle's contents for unblinding.

The study blind will be broken on completion of the clinical study and after the study database has been locked.

- Investigators will be made aware of their subject treatment assignments at the completion of the study.

During the study, the blind may be broken **only** in emergencies when knowledge of the participant's treatment group is necessary for further participant management. When possible, the Investigator should discuss the emergency with the Medical Monitor prior to unblinding. During the study, the blind may be broken to the designated unblinded study staff **only** in emergencies when knowledge of the participant's treatment group is necessary for further participant management.

## 8.3 Formulation of Test and Control Products

### 8.3.1 Formulation of Test Product

Syntocinon is a formulation of oxytocin, developed originally by Novartis Pharmaceuticals, for intranasal administration to stimulate of milk ejection and prevent of mastisis. Syntocinon is a clear colorless solution that requires no reconstitution. See Table for formulation and measured pH of Syntocinon and Placebo.

Oxytocin and placebo will be ordered from one of the following manufacturers/pharmacies depending on supply and ability to guarantee prompt and cooled shipment:

1. Wellspring Compounding Pharmacy, Berkeley, CA – licensed pharmacy which produces research drugs to many large hospitals and research centers in the San Francisco Bay Area. Use of USP pharmaceutical grade chemicals in a State of California licensed sterile compounding facility.

If the shipment arrives in larger bottles (not packaged for individual-use), Abbotts Pharmacy, or designated study staff will repackage the oxytocin & placebo solution into smaller bottles

---

containing 40 IU/1ml of oxytocin or placebo. Abbotts Pharmacy or designated study staff, who will not be present during the study sessions and will not be involved with running anyof the study sessions, will be responsible for repackaging the drugs and keeping track of each bottle's contents for unblinding. All labels indicating that the drug is oxytocin or placebo will be removed.

Table 1: Wellspring Pharmacy Formulation and Measured pH of Oxytocin and Placebo

	Oxytocin	Placebo
Active Ingredient, mg/mL	Oxytocin USP 40 IU/ml	Water
Other ingredient, mg/mL	0.05% methylparaben 0.025% propylparaben Distilled water	0.05% methylparaben 0.025% propylparaben
pH	4 – 4.5	

### **8.3.2 Formulation of Control Product**

A placebo solution will be provided by one of the three manufacturers/pharmacies described above in amber glass bottles with a nasal spray pump applicators and caps ready for administration. The formation for the placebo is listed in Tables 1 and 2. If the shipment arrives in larger bottles (not packaged for individual-use), Wellspring Pharmacy or designated study staff will repackage the nasal sprays into individual syringes (to be administered with nasal spray atomizers) and remove any labels that the vendors have placed

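### Section 8.3.2 puts bulk-shipped placebo into syringes where four other sections specify bottles; separately, 4.1 and 8.4.1 call the placebo saline, against the Table 1 vehicle

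*Combined protocol and SAP*

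**What the plan says.** **Device.** Section 8.2 sets the aim that "the identity of test and control treatments will not be known to investigators, research staff, or participants" and rests it partly on the container: "Packaging and labeling of test and control treatments will be identical to maintain the blind". It continues: "The oxytocin or placebo will be repackaged into smaller bottles containing 1 mL of either the oxytocin or placebo". For bulk shipments, 8.3.1 agrees: "Abbotts Pharmacy, or designated study staff will repackage the oxytocin & placebo solution into smaller bottles". Section 8.3.3 also gives glass bottles with pump applicators for that case. The instructions in 8.4.3, for both the acute and the three-week phase, describe an upright bottle whose nozzle goes into the nostril.

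Section 8.3.2, on the control product, supplies placebo in amber glass pump bottles by default. For shipments in larger bottles it departs from the other sections: the instruction is to "repackage the nasal sprays into individual syringes (to be administered with nasal spray atomizers".

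**Vehicle.** Table 1, in 8.3.1, lists the oxytocin vehicle as "0.05% methylparaben 0.025% propylparaben Distilled water". Its placebo column has water and the same two parabens at the same percentages, with no sodium chloride. Section 8.3.2 refers the reader to the tables for the placebo formulation: "The formation for the placebo is listed in Tables 1 and 2". The treatment list in 4.1 and the dosing text in 8.4.1 call the placebo saline.

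**The concern.** The protocol gives whoever repackages a bulk shipment two incompatible instructions, and the one that stands apart is in the section on placebo. In the fMRI phase each participant receives oxytocin at one of Visits 2 and 3 and placebo at the other, with study staff giving the spray (8.4.3). In the three-week phase coordinators watch dosing by video (8.6). A syringe used only for placebo would be visible to participants and staff at each of these points. Because of the crossover, a participant could compare the two devices directly. That would defeat the safeguard on which 8.2 relies, for the SFS and for interview-rated outcomes such as the CAINS.

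The vehicle is a separate matter. It does not touch the packaging rule, but it decides what the comparison means. With the Table 1 placebo, the listed ingredients differ only by oxytocin. With a saline placebo, the contrast would be oxytocin in its paraben vehicle against saline, and oxytocin would no longer be isolated.

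**Working it through.** The plan states no figure on this point and no arithmetic applies. The check is a comparison of the text.

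**Container when product arrives in bulk**

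- 8.2: 1 mL bottles, both products, packaging identical.
- 8.3.1: smaller bottles, both products named.
- 8.3.3: glass bottles with pump and cap, for the nasal sprays in general.
- 8.4.3: bottle and nozzle, both phases.
- 8.3.2: individual syringe with atomizer, in the control-product section.

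That is four sections for a bottle and one for a syringe. There are three ways to act on the text:

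1. Syringes for placebo only. This breaks the identical-packaging rule in 8.2.
2. Syringes for both products. The two would match each other, but this contradicts the bottles of 8.2, 8.3.1 and 8.3.3, and the 8.4.3 instructions would not fit the device.
3. Bottles for both products. This meets 8.2, 8.3.1, 8.3.3 and 8.4.3, and requires ignoring the clause in 8.3.2.

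No reading satisfies all five sections. The third satisfies the most and is probably what was meant.

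**Placebo composition**

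- 4.1: saline.
- 8.4.1: saline.
- Table 1: water, 0.05% methylparaben, 0.025% propylparaben.
- Oxytocin vehicle in Table 1: distilled water, 0.05% methylparaben, 0.025% propylparaben.

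Two sections say saline. The only formulation table gives a vehicle that matches oxytocin on its listed ingredients. The match goes no further than that list: the table as available shows one pH entry (4 to 4.5) and no separate placebo value, so equality of pH cannot be confirmed.

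**Reach.** The device conflict arises only for placebo that arrives in bulk. The documents do not give that share, and it may be zero. Section 8.2 does, however, describe repackaging into smaller bottles without any condition, and 8.4 says that unpredictable supply led to alternative manufacturing options. Repackaging is therefore an expected route.

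**The case against.** The strongest reply is that 8.2 governs blinding and is unconditional. It requires identical packaging, puts both products in 1 mL bottles, and assigns repackaging to staff who are absent from the sessions. The syringe clause covers bulk shipments only. It speaks of the nasal sprays, as 8.3.3 does, and ends with the same label-removal step, so it may be leftover wording that was meant for both products. On this view, harm would require staff to apply the clause to placebo alone, against three other sections. For the vehicle, saline appears only in an overview and a dosing paragraph, while 8.3.2 sends the reader to the tables. Table 1 is also titled for one pharmacy, and 8.4 allows for others, so a different formulation from another supplier cannot be excluded.

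Most of this stands, and it keeps the point minor. It does not remove the conflict. These are operating instructions, and the protocol does not say which section prevails. If another supplier's placebo really is saline, the comparator depends on the supplier, and the protocol should say so.

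A reader might also infer that participants given a syringe or saline placebo should be left out of a sensitivity analysis. That does not follow. In the three-week phase only the placebo arm takes placebo, so the exclusion would remove people from one arm after randomisation. In the crossover everyone takes placebo, so it could remove every participant.

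**Conclusion.** The concern holds as an internal inconsistency of minor severity. The current text contains two conflicts: syringe against bottle for bulk-shipped placebo, and saline against the paraben-water vehicle for placebo composition. That the conflicting text exists is certain. Its consequences are conditional: the blind is at risk only if the syringe clause is followed for placebo alone, and the comparator changes only if saline was actually supplied.

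A reader might infer that the blind was broken, or that participants could tell saline from paraben water. The documents support neither. Nothing shows that a mismatched device or vehicle was dispensed, and nothing in them bears on whether the two liquids can be told apart. Nor can a size of effect on SFS or rTPJ activation be given. A count of doses or of preservative exposure would describe contact with a product under assumptions about supply. It would not measure bias.

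Three related slips are clerical and carry no weight here. Section 8.3.2 names Wellspring as repackager ("Wellspring Pharmacy or designated study staff will repackage the nasal sprays into individual syringes") where 8.3.1 and 8.3.3 name Abbotts, and all three allow designated staff instead. Section 8.3.2 cites a Table 2 that does not appear. Sections 8.3.2 and 8.4 refer to three suppliers where 8.3.1 lists one.

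**What to change.** 1. In 8.3.2, replace the syringe clause with the bottle wording of 8.3.3 and say that it applies to both products. The wording in 8.3.3 gives the dose as 40 IU per 1 mL, which describes oxytocin only, so state the fill as 1 mL in identical pump bottles.
2. In 4.1 and 8.4.1, replace saline with the Table 1 vehicle.
3. Check the supply and repackaging records for the container and formulation actually dispensed. Section 8.5 mentions only numbers dispensed and returned, so the contents log described in 8.2 may also be needed. The designated staff who hold that log should do the check, so that the blind is kept until database lock.
4. If a different device or vehicle was used, report it as a limitation of the blinding or of the comparator. Do not add an analysis that excludes the participants concerned.
5. At the same time, correct the repackager name, the reference to Table 2 and the references to three suppliers.

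The cost is a few wording edits, with the IRB approval that 14.1 requires for amendments, and one check of records. Sample size, visits and the primary model do not change.
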